1.1.1 Catheter ablation of atrial fibrillation and guidelines

Catheter ablation has become a standard therapy for managing AF, particularly in patients with symptomatic paroxysmal or persistent AF who have failed medical therapy. Pulmonary vein isolation (PVI) remains the fundamental strategy for catheter ablation, and PVI is endorsed by guidelines from the European Society of Cardiology (ESC), American Heart Association (AHA), and Heart Rhythm Society (HRS) as the first-line approach for AF ablation^{1, 2}.

New innovations such as **contact force-sensing catheters**, **3D electroanatomic mapping systems**, and **ICE** have improved catheter positioning, lesion precision, and procedural safety. In addition, Recent technological advancements have further optimized the safety and efficacy of AF ablation. **PFA**, a novel non-thermal ablation modality, uses electroporation to selectively ablate myocardial tissue while sparing adjacent structures such as the esophagus, phrenic nerve, and pulmonary veins. PFA has demonstrated potential for shorter procedure times and reduced risks of complications, offering a promising alternative to conventional thermal ablation techniques³⁻⁶.

These advancements, combined with the established efficacy of PVI, are driving improvements in the outcomes and safety of catheter ablation procedures, addressing unmet needs in AF treatment, and broadening the scope of patients who can benefit from this therapy.

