3.4.2 Secondary endpoints

[figure not shown]
- The acute success of the procedure.
- The proportion of intraoperative conversion to using X-ray.
- Utilization of lead personal protective equipment (PPE) and wear time.Well-being survey of staff.
- The proportion of patients with recurrence of targeted arrhythmia during the first 90 days post-ablation.
- Early recurrence of atrial arrhythmias, defined as any AF/AFL/AT episode lasting >30 seconds occurring during the blanking period.
- Late recurrence of atrial arrhythmias, defined as any documented AF/AFL/AT episode lasting >30 seconds occurring after the blanking period and up to 12 months.
- Impact of early recurrence on late recurrence, assessed through survival analysis and multivariable adjustment to evaluate whether early recurrence predicts subsequent late recurrence.
- AF burden, assessed by scheduled rhythm monitoring (e.g., 7-day Holter at 3, 6, 9, and 12 months), expressed as the proportion of time spent in AF during the monitoring period.
- Incidence of peri-procedural complication.
- Total procedure duration, ablation time.
- changes in quality-of-life (using the AF Effect on Quality of Life (AFQT) and the EuroQol Health-Related Quality-of-Life 3-Level (EQ-5D-3L)).

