Given the increasing adoption and availability of pulsed field ablation (PFA) in current clinical practice, and in order to maintain the external validity of the study in the future era when PFA is expected to become the predominant ablation modality, the study adopts a population-level expectation for patients enrolled after the effective date of this protocol version:

Without influencing individual clinical judgment, the cumulative proportion of PFA among subsequently enrolled patients is expected to progressively increase, with a target of achieving $\geq 50\text{-}60\%$ of all newly enrolled cases.

This expectation aims to optimize the overall energy composition of the study cohort to better reflect evolving clinical practice trends. It does not impose restrictions on individual patient-level energy selection and does not apply to participants enrolled prior to the implementation of this protocol amendment.

Recommendations

- 1) The configuration of the Non-fluoroscopic Lab needs to be in accordance with the latest expert consensus recommendations (Jiang C, et al. Pacing Clin Electrophysiol. 2023 Sep;46(9):1035-1048).

- 2) The use of ICE catheter is required for both groups. The application of ICE technology includes but is not limited to: visualizing the cardiac anatomy; guiding catheter placement, transeptal puncture (if necessary); constructing the geometry; monitoring intracardiac thrombus and cardiac effusion throughout the procedure.
- 3) Magnetic mapping catheters (e.g. Lasso, PentaRay, or DECANAV) is recommended to create the cardiac geometry.
- 4) A safe, rapid, and smooth plan for transfer to the DSA lab should be established if no mobile DSA equipment is available in the Non-fluoroscopic EP Lab. In the event of an emergency requiring the use of DSA, patient transfer should be completed in a minimum period to maximize patient safety.
- 5) If deemed necessary, X-ray imaging may be utilized to guide catheter placement and monitor for potential complications. The use of X-ray must adhere to the As Low As Reasonably Achievable (ALARA) principle, ensuring radiation exposure is minimized while maintaining procedural safety and effectiveness.

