7.5.4 SUSARs Reporting

Suspected Unexpected Serious Adverse Reactions [SUSARs] will undergo expedited reporting to relevant regulatory authorities (e.g., research ethics committees, National Medical Products Administration, and National Health

Commission of the People's Republic of China). Investigators must report all SUSARs to sponsor as soon as possible and 24h of learning of the event. These SUSARs will be centrally reviewed and reported by the sponsor as soon as possible:

For fatal or life-threatening SUSARs, sponsor must report as soon as possible and within 7 days of learning of the events. Active follow-up must be completed within the following 8 days (The first day of learning of the event is considered 0 day).

For fatal or life-threatening SUSARs, sponsor must report as soon as possible and within 15 days of learning of the events.

8. Statistical analysis

Continuous variables are expressed as mean \pm SD if normally distributed or median (interquartile range [IQR]) if not normally distributed. Intergroup differences will be compared by student's t-test (normally distributed data with equal variance) or Mann-Whitney U test (failed either normality or equal variance test). Categorical variables will be presented as percentages and compared by using the Chi-square test or Fisher's exact test. The Kaplan-Meier method will be used to describe event-free rates over time. The statistical significance for all tests will be accepted at $P < 0.05$.

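### The unadjusted, pre-test-driven comparison fixed in Section 8 is inefficient for procedure duration and ablation time, and its rank test does not estimate mean lab time

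*Protocol*

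**What the plan says.** Section 8 sets one rule for all continuous variables. The groups are compared by "student's t-test (normally distributed data with equal variance"), "or Mann-Whitney U test (failed either normality or equal variance test"). The summary is the mean with SD, "or median (interquartile range [IQR]) if not normally distributed". The rule has no covariate, and Section 8 mentions neither a difference nor a confidence interval.

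Section 3.4.2 lists "Total procedure duration, ablation time" among the secondary endpoints, so the rule covers both. The same list has "The proportion of intraoperative conversion to using X-ray".

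Three other places bear on the choice:
- Section 1.1.1 states that "PFA has demonstrated potential for shorter procedure times and reduced risks of complications".
- Section 3.7 has the investigator choose RF or PFA before randomisation, with PFA expected to reach at least 50-60% of new cases. Section 6.5 requires the modality to be documented for every enrolled case.
- Section 3.7 allows X-ray in the non-fluoroscopic arm when needed. For emergencies where no mobile DSA equipment is available, it provides for transfer to the DSA lab.

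**The concern.** Two features of the design sit badly with this rule for time outcomes.

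First, energy modality is a known baseline factor that may shift procedure time and is present in both arms. An unadjusted test counts the RF-PFA difference as noise, whichever branch the pre-tests select.

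Second, if a few Group 1 cases convert and run long, mean lab time and typical case time can part company. Section 1.2.2 asks whether the non-fluoroscopic lab is cost-effective and Section 3.2 hypothesises reduced costs. Lab cost follows total, hence mean, time. Mann-Whitney with medians addresses which arm's cases tend to rank higher and does not estimate mean minutes.

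At stake is the between-lab comparison of two secondary endpoints.

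**Working it through.** The protocol gives no power figure for these endpoints, so there is nothing to reproduce first.

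**Inputs.** From the protocol: 362 per arm (Section 3.5), P<0.05 (Section 8, taken as two-sided), modality chosen before randomisation and PFA expected at 50-60% (Section 3.7; 55% used here). Assumed, because the protocol does not give them: mean 90 min and SD 20 min within a modality, a 5-min lab difference, an RF-PFA gap of 10-60 min, and the conversion rates and delays below.

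**Step 1: cost of leaving out energy modality.** With RF-PFA gap g:

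- within-arm variance = 20² + 0.55 × 0.45 × g²
- SE of the difference = SD × √(2/362)
- power = Φ(5/SE − 1.96)

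For g = 60: variance = 400 + 0.2475 × 3600 = 1291, SD = 35.9, SE = 2.67, power = Φ(1.87 − 1.96) = 46%. With modality in the model the residual SD is 20 at any gap: SE = 1.49, power = Φ(3.36 − 1.96) = 92%.

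| RF-PFA gap (min) | SD | SE | t-test, no covariate (formula) | Mann-Whitney (simulated) |
|---|---|---|---|---|
| 10 | 20.6 | 1.53 | 90% | 88-89% |
| 30 | 25.0 | 1.86 | 77% | 71-74% |
| 40 | 28.2 | 2.10 | 66% | 60-62% |
| 60 | 35.9 | 2.67 | 46% | 44-48% |

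The simulated energy-adjusted model with robust errors stays at about 91-93% throughout, with type I error of 3-6%. The first two methods lie within a few points of each other, so most of the gain comes from the covariate and little from replacing Mann-Whitney by Welch.

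**Step 2: conversions in Group 1 only.** A share c converts and each adds d minutes, with equal routine times. The mean difference is c × d, and its SE is √[(800 + c(1 − c)d²)/362].

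- c = 5%, d = 60: difference 3 min, SE = √(971/362) = 1.64, Welch power 45%.
- c = 5%, d = 120: difference 6 min, SE = √(1484/362) = 2.02, Welch power 84%.

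For the rank test, the chance that a Group 1 case outlasts a Group 2 case cannot exceed 0.95 × 0.5 + 0.05 × 1 = 0.525, however long the delay. Its null SE is √[725/(12 × 362²)] = 0.0215, so z is at most 0.025/0.0215 = 1.16 and power is capped near Φ(1.16 − 1.96) = 21%. Simulation agrees: 19-22% for the rule as written, against 42-45% (d = 60) and 85-87% (d = 120) for Welch.

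Now set the means equal. Let routine Group 1 cases average 84 min and converted cases 204: 0.95 × 84 + 0.05 × 204 = 90. The ranking probability is 0.95 × Φ(−6/28.3) + 0.05 × 1.0 = 0.445, so z = −2.55, and Group 1 is called faster in about Φ(2.55 − 1.96) = 72% of trials. For delays of 60 to 120 min, simulation gives 13-14% rising to 72-77%, against 4-6% for Welch.

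Other assumptions give the same pattern. With a lognormal time (median 120 min, log-SD 0.25), 5% converted and +240 min, the mean penalty of 12 min is detected in 21% of trials by Mann-Whitney and in 94% by Welch. With routine cases 10 min faster, 10% converted and +180 min, the Group 1 mean is about 8 min longer, yet Mann-Whitney calls Group 1 significantly faster in 35-42% of trials.

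**Step 3: where the difference disappears.** With equal means, 1-2% converted at +20 to +60 min, or 5% at +20 to +30 min, gives Mann-Whitney rejection of 4-6%, the same as Welch. With equal routine times, the largest power gap in those settings is 8% against 13% (2% converted, +60 min).

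**Step 4: unequal spread alone.** With equal arms and symmetric data, Mann-Whitney's type I error is 5.5% at an SD ratio of 2 and 7.3% at a ratio of 3. This is a minor matter here.

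**The case against.** The strongest reply is that covariate adjustment and interval estimates for secondary endpoints are commonly left to the statistical analysis plan, which was not available here. That stands as far as it goes: a missing covariate in a protocol would not by itself be a finding. The point is narrower. Section 8 does not leave the method open. It names an unadjusted rule for all continuous outcomes.

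The second reply is that the conversion scenario is assumed, and this stands in full. The protocol states no conversion rate, no added time and no definition of whether transfer time counts. Transfer is foreseen for emergencies without mobile equipment, other X-ray use may be brief, and patients scheduled for procedures needing fluoroscopy are excluded. Conversion proportion is also reported separately, so such cases are not hidden.

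Third, Mann-Whitney is a legitimate way to ask whether a typical case is shorter. In the equal-means scenario 95% of Group 1 cases really are faster, so its rejections are not false for that question. Mean against typical time is a choice of estimand.

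A reader might infer more than the documents support:
- That the rank test ignores converted cases. They are ranked, and their length counts until they exceed nearly all control cases.
- That it misleads in either direction. If long conversions occur only in Group 1, both errors favour the non-fluoroscopic lab. Nor does the protocol say that Group 2 has no long cases; a tail there would offset or reverse the effect.
- That unequal variances invalidate the test. Step 4 shows little effect with equal arms.
- That Welch must replace the rule for every continuous outcome. That is a preference.

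**Conclusion.** The point holds for procedure duration and ablation time.

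The firmer part is efficiency. Under the assumptions of Step 1, ignoring modality cuts Mann-Whitney power for a 5-min lab difference from about 88% at a 10-min RF-PFA gap to about 44% at 60 min, while adjustment holds it at about 91-93%. If RF and PFA times turn out close, little is lost. The protocol gives no size for the gap, only that PFA may be quicker.

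The conditional part is the estimand. The rank test does not estimate mean lab time. This has practical consequences only if about 5% or more of Group 1 cases convert, each adds an hour or more, and that time is counted. In that case a real mean penalty can be missed, or an advantage shown when means are equal, both to the benefit of the non-fluoroscopic lab. With rarer or shorter conversions the tests nearly agree.

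The matter is confined to secondary endpoints. The primary analysis and the sample size of 724 are untouched.

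**What to change.** Add to Section 8: *Total procedure duration and ablation time are compared over all randomised procedures, conversions included, by the difference in means with 95% CI from a linear model with lab and the energy modality chosen before randomisation, with robust standard errors and without normality or variance pre-tests. Medians (IQR) and Mann-Whitney tests are descriptive or supportive.*

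The model should use the modality recorded before randomisation, which keeps it a baseline covariate. It would help to say at the same time whether transfer time counts in procedure duration.

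The cost is one sentence in Section 8, settled before results by arm are seen. No new data are needed, since modality is already documented for every case. The downside is that a few very long cases widen the confidence interval of the mean. The rule for other continuous outcomes can stay.

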3.2 Study Rationale and Objective

This randomized controlled trial aims to evaluate the **efficacy, peri-procedural safety, and clinical outcomes** of catheter ablation performed in non-fluoroscopic EP labs compared to procedures in conventional DSA lab.

With the rapid adoption of non-fluoroscopic EP labs in China, it is essential to assess their performance to ensure safe and effective care. We hypothesize that non-fluoroscopic procedures will demonstrate non-inferior safety and efficacy to fluoroscopy-guided ablations, while offering benefits such as reduced costs, minimized radiation exposure for physicians, and improved environmental sustainability.

This study will provide evidence to guide clinical practice, improve patient care, and support the broader adoption of non-fluoroscopic EP technologies, enhancing access to advanced arrhythmia treatments and optimizing outcomes for patients with AF.

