3.5 Sample Size

For **efficacy** as the primary endpoint, sample-size was calculated by non-inferiority log-rank test with 1:1 design. The expected recurrence rate of AF is 30% for control group based on previous studies and our experience, and a hazard ratio of 1.3 was used for establish non-inferiority. Based on a power of 80% and an alpha of 0.05, proportion lost to follow up 5%, a sample size of **724 patients (362 for each group)** was estimated.

Safety endpoints will still be collected in detail and analyzed for comparison between the groups, but they will not be used to determine the sample size.

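### Section 8 accepts P < 0.05 for every test while the secondary endpoints have no order, correction or exploratory label, so secondary lab differences can be declared significant at full alpha whatever the primary result

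*Protocol*

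**What the plan says.** Section 8 (Statistical analysis) describes the t-test, Mann-Whitney, chi-square, Fisher and Kaplan-Meier methods and closes with a single threshold: "The statistical significance for all tests will be accepted at" P < 0.05. No comparison is exempted.

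The synopsis has 12 secondary bullets. Section 3.4.2 has the same 12 items in 11 bullets, because the staff well-being survey is run into the bullet on lead protective equipment. Neither list gives an order, an adjustment or a label.

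Labels are used elsewhere. Sub-analysis 1 (8.1.1) is called post-hoc, and sub-analyses 2 and 3 (8.1.2, 8.1.3) are called exploratory.

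Two of the items in 3.4.2 nearly coincide: "The proportion of patients with recurrence of targeted arrhythmia during the first 90 days post-ablation" and "Early recurrence of atrial arrhythmias, defined as any AF/AFL/AT episode lasting >30 seconds occurring during the blanking period". Section 3.4.1 sets the blanking period at 3 months, and the first item carries no 30-second rule.

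The sample size in Section 3.5 rests on primary efficacy alone: "Based on a power of 80% and an alpha of 0.05, proportion lost to follow up 5"%.

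**The concern.** A threshold that covers all tests, next to a long unranked list, makes every secondary comparison able to carry a claim at full alpha. Because the sub-analyses are labelled exploratory or post-hoc and the secondary endpoints are not, a reader will take the secondary endpoints to have a higher standing.

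Nothing in Section 8 ties secondary testing to the primary result. A chance difference in procedure time, quality of life, AF burden or early recurrence could be reported as a significant finding for or against the non-fluoroscopic lab, even if primary non-inferiority were not shown.

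**Working it through.** **1. The plan's own figure.** The protocol states no family-wise error rate. The only related figure that can be reproduced is the sample size, which shows where the stated alpha goes.

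- Inputs from the synopsis output table and Section 3.5: margin HR 1.3, true HR 1.00, hazard 0.30, loss 0.05, accrual 1, total time 3, power 80%, alpha 0.05, 1:1.
- Events = (z₀.₉₅ + z₀.₈₀)² / (0.25 × (ln 1.3)²) = (1.645 + 0.842)² / (0.25 × 0.0688) = 359.3.
- Event probability = (0.30/0.35) × [1 − (e^−0.70 − e^−1.05)/0.35] = 0.498.
- N = 359.3 / 0.498 = 721, against 723 in the table and 724 in the text.
- With a one-sided 0.025, N would be 916, which does not match.

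The stated alpha is therefore used in full, one-sided, on a single primary efficacy test. Secondary testing does not change that test's error rate. This step reproduces the plan's inputs and does not judge them.

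**2. How many secondary contrasts could be null.** Start from the 12 items.

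- Remove X-ray conversion and lead equipment use/wear time, which differ between the labs by design: 12 − 2 = 10.
- Remove the effect of early on late recurrence, which is not a comparison of labs: 10 − 1 = 9.
- Count 90-day recurrence and early recurrence once: 9 − 1 = 8.
- Split the two items that each hold two measures (procedure duration and ablation time; AFEQT and EQ-5D): 8 + 2 = 10.

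The ten are acute success, staff well-being, early recurrence, late recurrence, AF burden, peri-procedural complications, procedure duration, ablation time, AFEQT and EQ-5D.

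Two of these can be challenged. The staff questionnaire (Appendix E) asks about protective equipment, pain and radiation concern, so it may differ by design as well. Late recurrence largely restates the rhythm part of the primary endpoint. Without them, 10 − 2 = 8.

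**3. Chance of at least one false P < 0.05.**

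- Independent tests: 1 − 0.95^k. For k = 8 this is 0.337; for k = 10 it is 0.401.
- Correlated tests: Zᵢ = √ρ·C + √(1−ρ)·Eᵢ with standard normal C and Eᵢ, rejecting when |Zᵢ| > 1.96, over 400,000 draws.

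| Null contrasts | ρ = 0 | ρ = 0.5 | ρ = 0.8 |
|---|---|---|---|
| 8 | 33.7% | 25.0% | 15.8% |
| 10 | 40.1% | 28.8% | 17.3% |

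The range is about 3 to 8 times 5% (0.158/0.05 = 3.2; 0.401/0.05 = 8.0). The expected number of false positives is 0.05k, that is 0.4 to 0.5, whatever the correlation.

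**The case against.** The strongest reply is that only the protocol is at hand. Handling of multiplicity for secondary endpoints commonly sits in the SAP, and the sentence in Section 8 may be no more than a routine nominal threshold. Part of this stands: the missing hierarchy is not a finding in itself, and the protocol nowhere says that secondary results will be presented as confirmed. But the protocol does more than stay silent. It sets one threshold for all tests, and Section 6.1 says that the sponsor analyses the data as the protocol defines. A SAP that added a hierarchy would have to depart from the Section 8 sentence, so that sentence is the one to correct.

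Stronger readings are tempting but lack support:

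- **A false finding is likely, or the rate is 46%.** A reader might take all 12 items as independent tests (1 − 0.95¹² = 46%). Three of the items are not null lab contrasts and two nearly coincide, so 12 is not the right count. At 16–40%, at least one false finding is a material risk but not the more probable outcome. No single figure in that range can be presented as the protocol's own, because it gives neither a count nor a correlation.
- **The protocol already intends secondary claims.** A reader might infer this from Section 3.2, which hypothesises non-inferiority "while offering benefits such as reduced costs, minimized radiation exposure for physicians, and improved environmental sustainability". None of those benefits is among the 8 to 10 contrasts. Cost and sustainability are not listed secondary endpoints, and the nearest proxies for radiation are the items set aside as differing by design.
- **The main conclusion is compromised.** It is not; the primary efficacy test is a single comparison with its own error rate.

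**Conclusion.** The point holds as a defect in a stated rule, limited to secondary claims. Under Section 8 as written, any secondary lab difference with P < 0.05 counts as significant, with no condition on the primary result.

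The size rests on three assumptions: 8 to 10 contrasts that are truly null, two-sided tests at 5% (the protocol does not state sidedness), and one common correlation between the test statistics. That last assumption is a simplification for measures as different as staff well-being and AF burden. The lowest figure, 16%, is still about three times the per-test level.

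The change should be made because it is cheap and prevents over-reading of secondary results. It does not bear on the validity of the primary efficacy analysis.

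**What to change.** In Section 8, limit the P < 0.05 sentence to the primary analysis and add text to this effect:

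> Secondary endpoints are reported as estimates with 95% confidence intervals. Their P values are nominal and support no claim of significance. Any secondary endpoint intended for a claim is named here and tested with the Holm procedure at a family-wise two-sided 5%, only after primary non-inferiority has been shown.

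The wording must not make primary efficacy the only confirmatory comparison by default. The synopsis and Section 3.4.1 name a primary safety endpoint, and Sections 1.2.1 and 3.2 hypothesise non-inferiority on safety. Section 3.8.1 says only that safety does not drive the sample size. The new text should keep that endpoint as primary and state its own inferential status.

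As an editorial tidy-up only, merge the 90-day and early-recurrence items into one under the >30-second definition. This does not alter the figures above, which already count them once.

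Cost: a few sentences in Section 8 and the secondary endpoint lists (synopsis and 3.4.2), with no new data and no change to the sample size. The downside is that nominally significant secondary results can no longer be presented as confirmed, and the sponsor must choose in advance any on which it wants a claim.
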